11.1.4.1.1 Adverse Events of Special Interest (AESI)

Adverse events of special interest (AESI) will include the following:

- Infusion site reactions
- Cases of hypersensitivity (e.g. diffuse skin rash, anaphylaxis and angioedema).
- Polyneuropathy

11.1.4.1.2 Analyses of Infusion Site Reactions

• Summaries for total infusion site reactions, both as number of events, event rates adjusted to exposure and patient counts and percentages will be provided.

11.1.4.1.3 Hypersensitivity Analyses

- Summaries for total number of hypersensitivity cases (by SOC and PT), will be presented as number of events, event rates adjusted to exposure and patient counts and percentages.
- Time to onset of hypersensitivity will be presented by Kaplan Meier figures. In these analyses, the patients who did not experience hypersensitivity will be right censored at the time of the last visit.

- Time from onset of hypersensitivity to resolution will be presented with descriptive statistics. Unresolved cases will be right censored at the last visit.
- Summaries for total number of hypersensitivity will be broken down by outcomes (unknown, recovered, not yet recovered, recovered with sequelae and death) and will be presented as number of events, event rates adjusted to exposure and patient counts and percentages.

11.1.4.1.4 Polyneuropathy Analyses

- Summaries for total number of polyneuropathy cases (by SOC and PT), will be presented as number of events, event rates adjusted to exposure and patient counts and percentages.
- Time to onset of polyneuropathy will be presented by Kaplan Meier figures. In these analyses, the patients who did not experience polyneuropathy will be right censored at the time of the last visit.
- Time to from onset of polyneuropathy to resolution will be presented with descriptive statistics
- Summaries for total number of polyneuropathy will be broken down by outcomes (unknown, recovered, not yet recovered, recovered with sequelae and death) and will be presented as number of events, event rates adjusted to exposure and patient counts and percentages.

11.1.4.1.5 VAS Score for Pain

The VAS pain score will be summarized with descriptive statistics by visit and treatment group. In addition, the changes from baseline will be summarized. Furthermore, the proportion of patients with a VAS pain score >0 mm or \geq 40 mm will be tabulated by visit and treatment group.

11.1.4.1.6 Tolerability

Tolerability will be assessed based on percentage of subjects that complete the 12month treatment period (or long-term extension) of the study and the percentage of subjects who discontinue from the 12-month treatment period (or long-term extension) due to a TEAE. Time (days) from enrolment to discontinuation will be illustrated as Kaplan-Meier curves by treatment regimen. Patients who complete the study will be right censored at the date of last dose of study treatment during the 12-month study period (or long-term extension). Time to discontinuation will also be explored by recruitment wave 1 and 2 following corrective actions for patients' retention.

Local safety expressed by erythema, edema and Draize scores as well as assessment of nodules and hematomas (number and severity) will be listed but not summarized.

The safety data from the treatment extensions up to Month 102 will be combined with the safety data of the main study and will be analyzed similarly as defined above.

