For both cohorts, if required, subjects and their study partners will be trained and assisted at their homes during the first week of treatment by the Home Nursing Service on the correct administration technique. One mandatory home visit will be performed during the first week, preferably on Day 3. Throughout the 12-month treatment period the Home Nursing Service will visit the subjects at their homes on a monthly basis.

For both cohorts, during the treatment period (up to Month 102), a helpline will be available for subjects/study partners to call at any time should they encounter any difficulties with the pump system.

The planned treatment duration for all regimens is 12 months with in-clinic visits at Week 1, Month 1, Month 2, Month 3, Month 4, Month 6, Month 9 and Month 12.

Subjects will be allowed to continue with study treatment for an optional treatment extension period of 24 more months in which clinic visits will be performed every 3 months to assess subject safety. Subjects will be offered another optional long-term treatment extension period up to Month 102. During this long-term extension period, clinic visits will continue to be performed every 3 months to assess subject long-term safety.

Safety follow-up visits will be performed 1, 2 and 3 months after the last SC administration of the study drug.

This will be the third study to assess the administration of the ND0612 solution using different dosing regimens in a home setting, with the focus of the current study being on the safety of long-term home administration. Additionally, the study will explore the need for dose adjustments e.g., up and down titrations of the study drug and/or a need for additional oral anti-PD treatment.

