Additional safety visits will be scheduled for all subjects 2 and 3 months after the last study dose. This will be Month 14 and Month 15 for subjects with treatment up to Month 12 who chose not to continue to the optional treatment extension period. For subjects stopping treatment at Month 36 after the optional treatment extension, such visits will be scheduled at Month 38 and Month 39. For subjects stopping treatment at Month 102 after the optional long-term treatment extension period, such visits will be performed at Month 104 and Month 105. In case of early termination, these visits will be performed 2 and 3 months after early termination.

Assessments will be limited to:

• Urine pregnancy test for female subjects of childbearing potential if required by local legislation.

• Infusion site assessments will be performed and infusion site reactions will be reported as AESI (see Section 10.1.3)

9.2.6 Optional Treatment Extension Period (Visits Months 15, 18, 21, 24, 27, 30, 33, 36)

Subjects will be allowed to continue with study treatment for an optional treatment extension period of 24 more months in which clinic visits will be performed every 3 months.

Assessments will be limited to:

- Urine pregnancy tests for female subjects of childbearing potential will be performed at all clinic visits. The site will provide the subject with monthly home urine pregnancy kits. The subject will perform these tests at home on a monthly basis, and the site will contact the subject by phone and report the results of the monthly home tests on the source documentation.
- Vital signs (including supine [after resting for at least 5 min] and standing BP, pulse rate, and body temperature)
- Infusion site assessments will be performed and infusion site reactions will be reported as AESI (see Section 10.1.3)
- Blood test for vitamin B6, vitamin B12 and folate (Months 18, 24, 30, 36 only)
- Recording of AEs including SAEs and AESIs
- Home diary "ON/OFF" diary entries will be reviewed for completeness and accuracy
- New home "ON/OFF" diary will be dispensed (at Months 15, 21, 27, and 33 only). New pump diary will be dispensed at every extension period visit (Months 15, 18, 21, 24, 27, 30, and 33).
- Concomitant medication review (including anti-PD medication).
- Subjects will be provided with infusion sets, syringes and study medication sufficient for 1 month

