- Urine pregnancy tests for female subjects of childbearing potential will be performed at all clinic visits. The site will provide the subject with monthly home urine pregnancy kits. The subject will perform these tests at home on a monthly basis, and the site will contact the subject by phone and report the results of the monthly home tests on the source documentation.
- Vital signs (including supine [after resting for at least 5 min] and standing BP, pulse rate, and body temperature)

- Infusion site assessments will be performed and infusion site reactions will be reported as AESI (see Section 10.1.3)
- Blood test for vitamin B6, vitamin B12, and folate will be performed every 6 months from Month 42 up to 102 months, where applicable
- Recording of AEs including SAEs and AESIs
- Concomitant medication review (including anti-PD medication)
- Subjects will be provided with infusion sets, syringes and study medication sufficient for 1 month
- Drug accountability review of used and unused study medication (vials containing particles will be counted separately); subjects are to bring their supplies to all clinic visits
- Optional: in case the subjects did not complete the user experience questionnaire during the optional treatment extension period, they will be asked to complete it during the optional long-term extension period (see Section 10.3 and Appendix 17.14)
- Other assessments may be done at the investigator's discretion

As the clinic visits are more than 1 month apart, the site will dispense study drug and clinical supplies for 1 month to the subject, or the study partner at additional clinic visits dedicated to study medication dispensing. Alternative means for medication distribution (e.g., via courier) may be used following regulatory and EC approval.

In the long-term extension period, subjects will also be allowed to switch from Regimen 1 to Regimen 3, or from Regimen 3 to Regimen 1, according to the investigator's decision.

At the end of the long-term extension period visit (Month 102) subjects will return the infusion pump to the site and will be prescribed an appropriate commercial LD/DDI dose as determined by the investigator.

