10.1.2 Clinical Laboratory Evaluation

The safety laboratory tests will include hematology, blood chemistry, and dipstick urinalysis. Samples will be taken according to the schedule of assessments in Section 8.1.2 and as outlined in Section 9.

Laboratory tests will include:

Hematology: white cell count and differential count, red cell count, hemoglobin, hematocrit, mean cell volume, mean cell hemoglobin, mean cell hemoglobin concentration, platelet count

Clinical Chemistry: sodium, potassium, chloride, glucose, blood urea nitrogen (BUN), creatinine, calcium, phosphate, bilirubin, alkaline phosphatase, gamma glutamyl transpeptidase (gamma GT), AST, ALT, total protein, albumin, and cholesterol

Urinalysis: pH, protein, glucose, ketones, urine microscopic (if required): white blood cell count, red blood cell count, casts

In addition, blood tests for vitamin B6, vitamin B12 and folate will be performed during the extension periods according to the schedule of assessments in Section 8.1.2.

Urine pregnancy tests will be performed for all female subjects of childbearing potential according to the schedule of assessments in Section 8.1.2 and as outlined in Section 9.

Serology will be performed at the screening visit only to detect: Hepatitis B Surface Antigen (HBsAg), HCV and HIV.

The hematology and clinical chemistry laboratory analyses will be performed at a central laboratory (Covance Central Laboratory Services, see Section 2) with the following exception: Data from safety laboratory tests (blood chemistry, hematology, and dipstick urinalysis) will be analysed locally at the Month 103 Safety Follow-up visit (see Section 9.2.4) and for early termination visits during the long-term extension period (see Section 9.2.8).

Reference ranges will be used by the investigator to assess the laboratory data for clinical significance and pathological changes.

The total amount of blood sampled is 50 ml during the 12-month treatment period and an additional 82.5 ml during the optional extension periods, including the long-term extension period. The calculated amount excludes optional safety samplings at safety follow-up visits, early termination samplings, as well as repeat and unscheduled samplings.

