11 STATISTICAL METHODS

11.1 Statistical and Analytical Plans

The analyses related to the primary objective will include the study data up to the Month 12 visit. A separate analysis will be conducted based on the data up to 102 months. In addition, safety snapshot data in between the above-mentioned time periods may be summarized during the study conduct for regulatory purposes.

The analysis of the safety data will be based on data accumulated from the present study. For safety, Cohort 1 and Cohort 2 will be analyzed jointly (for Regimen 1) and separately. For efficacy, Cohort 1 and Cohort 2 will be analyzed separately (where applicable). Baseline values for Cohort 1 will be derived from the ND0612H-006 study.

The safety data will be summarized for both the total Safety Set and broken down by the treatment regimen (Regimen 1 or Regimen 3). An additional safety analysis will be conducted by excluding the safety data from the subjects who received Regimen 2 during the corresponding treatment period (i.e., the data captured after the first dose of Regimen 2 until the switch to Regimen 1 will be excluded).

A fully detailed Statistical Analysis Plan (SAP) will be produced and finalized after finalizing the protocol and before any data base lock. The SAP will detail the implementation of all the planned statistical analyses in accordance with the protocol. Any deviations from the statistical analyses planned in the protocol will be documented in the SAP and any deviations from the statistical analyses planned in the SAP will be documented in the final clinical study report.

All data will be listed. In general, data will be summarized using either descriptive statistics (number of non-missing observations, mean, median, standard deviation (SD), standard error of the mean (SEM), minimum and maximum for continuous data) or frequency counts and percentages for categorical data.

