11.1.4 Primary Analyses

11.1.4.1 Methods of Analysis

Adverse events will be coded using the Medical Dictionary for Regulatory Activities (MedDRA). Adverse events will be grouped by system organ class (SOC) and preferred term (PT) and summarized by treatment regimen. Only treatment emergent AEs (TEAEs) will be summarized. TEAEs are defined as all AEs that start or worsen on or after the start of first study drug administration in the present study and before the start of the optional treatment extension (for the 1-year analysis). It is assumed that AEs that started in study ND0612H-006 will not be recorded on the case report form of the present study (unless the event in question worsened during the present study), as these

events will not be TEAEs in the present study. For subjects who do not participate in the optional treatment extension, events that start >28 days after the last dose of study medication will not be defined as TEAEs.

The summary tables will present the frequency and percentage of total subjects and number of events, by SOC and by PT.

For the summaries of AEs, subjects who experience the same AE (in terms of the MedDRA PT) more than once will only be counted once for that event in the number of subjects but all occurrences of the same event will be counted in the number of events. In addition, separate summaries will be provided for AEs by severity and relationship to study drug, as well as separate summaries for AEs leading to study drug discontinuation and SAEs.

In addition to the frequency counts and percentages, the AEs will be presented as annualized rates. The annualized rates will be calculated by the total number of reported AEs divided by the total exposure time, measured as the total subject years of exposure to the study medication.

The below listed summaries will be produced for the Safety Set. In general, all safety endpoints will be summarized using either summary statistics or frequency tabulations, as applicable to the type of data.

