11.1.7 Handling of Missing Data

For the analysis of the AEs, the incomplete follow-up will be taken into account by summarizing the data as annualized rates in addition to the frequency counts and percentages. The analysis of the annualized rates takes into account the actual duration of the exposure to the study treatment.

For the efficacy analyses of continuous endpoints, likelihood-based modeling approach (MMRM) will be used to handle incomplete data.

All withdrawals will be included in all analyses up to the time of withdrawal. Subjects who are withdrawn prematurely from study drug and/or the study will be included in all analyses regardless of the duration of treatment. In general, there will be no imputation for missing data, unless otherwise specified.

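### The up-to-102-month AE rates pool all events over all exposure, although most scheduled safety tests lapse between Month 12 and exit; report the rates by period

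*Protocol*

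**What the plan says.** Protocol 11.1.4.1 defines the rate: "The annualized rates will be calculated by the total number of reported AEs divided by the total exposure time", the latter in subject-years on study medication. Protocol 11.1.4.1.6 carries this into the extensions: "The safety data from the treatment extensions up to Month 102 will be combined with the safety data of the main study", analysed as in the main study. SAP 3.5.2 and 7.1 repeat the instruction and leave the detail to a separate extension SAP. The only allowance for incomplete follow-up is in Protocol 11.1.7: "The analysis of the annualized rates takes into account the actual duration of the exposure to the study treatment".

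The visit content changes at Month 12. Both extension sections (Protocol 9.2.6 and 9.2.7) open their lists with "Assessments will be limited to". The lists keep vital signs, infusion-site assessment, concomitant medication and AE recording. They omit chemistry, haematology, urinalysis, ECG, C-SSRS, QUIP-RS and ESS. The 9.2.7 list, but not the 9.2.6 list, adds that "Other assessments may be done at the investigator's discretion". Vitamin testing runs the other way: Protocol 10.1.2 states that "blood tests for vitamin B6, vitamin B12 and folate will be performed during the extension periods", and no such draw is scheduled in the first 12 months. Home nursing is also tied to the first year: "Throughout the 12-month treatment period the Home Nursing Service will visit the subjects at their homes on a monthly basis" (Protocol 6.5).

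**The concern.** An exposure-adjusted rate is comparable across periods only if events are looked for in much the same way throughout the exposure in the denominator. Here the number of subject-years keeps growing after Month 12, while several of the routes by which AEs come to light are no longer scheduled. Protocol 10.1.1 counts an abnormal laboratory finding as a possible AE, so the numerator depends partly on testing.

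A 12-month rate printed next to a lower up-to-102-month rate for a laboratory, ECG, suicidality, impulse-control or sleepiness term invites the reading that risk declines with longer treatment. The pooled rate cannot separate that from less testing. Long-term safety to Month 102 is a stated objective (Protocol 7.2), so the misreading would matter.

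**Working it through.** The plan gives no rate, retention or exposure forecast, so there is no figure of its own to reproduce. The check has three parts.

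**1. Scheduled assessments before and after Month 12**

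| Assessment | First 12 months, from Day 2 on | Months 15-102, on treatment | At exit |
|---|---|---|---|
| Safety laboratory tests | 8 visits (Week 1; Months 1, 2, 3, 4, 6, 9, 12) | none scheduled | as needed at Follow-up 1; discretionary at extension early termination |
| ECG | same 8 | none scheduled | Follow-up 1; discretionary at extension early termination |
| QUIP-RS, ESS | same 8 | none scheduled | Follow-up 1 and early termination |
| C-SSRS | 6 (not Months 2 and 4) | none scheduled | Follow-up 1 and early termination |
| B6, B12, folate | none | every 6 months from Month 18 | not listed |

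Sources: Protocol 9.2.3 to 9.2.8, 10.1.2, 10.1.7 to 10.1.10.

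Scheduled visits with infusion-site assessment number 9 or 10 in year 1 (Day 1; Day 2 for Cohort 2; Week 1; seven monthly visits). Afterwards they are 3-monthly, that is 4 per year.

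**2. Blood volumes as a cross-check (Protocol 10.1.2)**

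- First 12 months: 50 mL / 10 planned laboratory visits (Screening, Day 1 and the 8 above) = 5.0 mL each.
- Extensions: 82.5 mL / 15 vitamin draws (4 from Month 18 to 36, 11 from Month 42 to 102) = 5.5 mL each.

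This fits an extension with vitamin draws and no scheduled safety laboratory tests.

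**3. Size of the understatement, under assumptions**

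Let the true event rate be constant. Let f be the share of extension events that are reported even though the tests are not scheduled. Let w be the share of all subject-years that falls in Months 0-12. Then

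- pooled rate / 12-month rate = w + f(1 - w);
- understatement = (1 - f)(1 - w).

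With N = 210 (Protocol 11.2), 12-month completion c, share e of completers entering the extension, annual extension drop-out d, and T years of extension (2 to Month 36, 7.5 to Month 102):

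- PY(0-12) = N(1 - c)/(-ln c);
- PY(extension) = N c e [1 - (1 - d)^T]/(-ln(1 - d)).

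Only N comes from the documents; c, e, d and f are assumptions.

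Worked example, c = 0.60, e = 0.90, d = 0.20: PY(0-12) = 210 × 0.40/0.511 = 164. PY(extension to Month 102) = 113.4 × (1 - 0.8^7.5)/0.223 = 413. So w = 164/577 = 0.285. The understatement is 72% with f = 0 and 36% with f = 0.5.

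| c / e / d (%) | PY 0-12 | PY ext. to M102 | w at M102 | M102, f = 0 | M102, f = 0.5 | M36, f = 0 |
|---|---|---|---|---|---|---|
| 100 / 100 / 0 | 210 | 1575 | 0.118 | 88% | 44% | 67% |
| 80 / 95 / 10 | 188 | 827 | 0.185 | 81% | 41% | 60% |
| 70 / 90 / 15 | 177 | 573 | 0.235 | 76% | 38% | 56% |
| 60 / 90 / 20 | 164 | 413 | 0.285 | 72% | 36% | 53% |
| 55 / 80 / 30 | 158 | 241 | 0.396 | 60% | 30% | 46% |
| 55 / 80 / 40 | 158 | 177 | 0.472 | 53% | 26% | 42% |
| 50 / 70 / 50 | 151 | 105 | 0.590 | 41% | 21% | 34% |

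For terms that rest on the vitamin tests the untested stretch is year 1. In the worked example the pooled rate would be 1 - 0.285 = 0.715 of the rate in the tested period, if no such event came to light earlier.

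**The case against.** The strongest reply has four parts.

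- **Testing does not end at Month 12.** Safety Follow-up 1 repeats ECG, C-SSRS, QUIP-RS and ESS. Early termination in the extensions repeats the Month 12 procedures, with laboratory tests and ECG discretionary. The long-term extension allows further assessments. This stands: a reader might infer that these tests stop for good at Month 12, and the documents do not say so. But one exit assessment after up to 7.5 further years does not match six or eight in year 1.
- **The long-term objective focuses on AESIs**: infusion-site reactions, hypersensitivity and polyneuropathy. These do not depend on ECG, the scales or routine chemistry. AEs are also elicited by open questioning, so many psychiatric or symptomatic events would surface anyway. This stands and limits the reach of the point.
- **Infusion sites remain under review.** A reader might take the drop from 9 or 10 scheduled visits to 4 per year as a proportional loss of infusion-site reactions. That is not supported. Protocol 10.1.3 requires assessment at all clinic visits, dispensing visits may fall between the 3-monthly ones, and subjects or their partners handle the sites daily. Only the change in scheduled frequency is established.
- **The plan already separates the periods in part.** Protocol 11.1 says "A separate analysis will be conducted based on the data up to 102 months", so the 12-month rates stand undiluted and a later rate could be obtained by subtraction. The extension SAP, not among the documents, may already present periods. That is possible, but the instruction it inherits is to combine and analyse similarly, and readers should not have to subtract.

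**Conclusion.** The point holds as one of presentation and interpretation in the up-to-102-month analysis. Following the plan, pooled rates of AEs found mainly by the year-1 tests will be understated relative to year-1 ascertainment, and nothing in the plan tells the reader so. The primary 12-month analysis is untouched.

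The direction is clear if the true rate is roughly constant and part of the events would be missed without scheduled testing. The size is open. With no other detection route the understatement at Month 102 is 41-88% over the assumed retention scenarios; with half of the events reported anyway it is 21-44%. At Month 36 with no other route it is 34-67%. It is tempting to say that these rates are cut by half or more. The documents do not support that as a general statement: it needs detection by the scheduled tests alone together with moderate or better retention, and it fails in every scenario here in which half of the events are still reported.

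**What to change.** In Protocol 11.1.4.1.6 and in the extension SAP, state that exposure-adjusted AE and AESI rates will be presented for Months 0-12, 12-36 and 36-102, each with its own events and subject-years, beside any pooled rate. Add a footnote to these tables that lists what changes at Month 12: safety laboratory tests, ECG, C-SSRS, QUIP-RS and ESS no longer scheduled until exit; scheduled infusion-site visits 3-monthly; monthly home nursing scheduled for year 1 only; vitamin tests starting in the extension. Say there that pooled rates of laboratory, ECG, suicidality, impulse-control and sleepiness terms are not to be read as a change in risk. The footnote is needed even with period rates, because a period split shows the change in detection but does not remove it.

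Keep all extension events in the tables. Restricting test-related terms to Months 0-12 is not advisable: the AE data items listed in Protocol 10.1.1 do not record how an event was found, and the restriction would drop events found at exit or by discretionary testing.

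The cost is one period variable in the AE tables and some wording. No new data are needed. Interval rates will be less precise than a pooled rate, most of all for Months 36-102 if few subjects remain.
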